In this randomized controlled trial, differences in overall stress, burnout and wellbeing will be assessed for employees participating in IEO, an online mind-body course that incorporates both meditation and yoga.

The following specific aims are to be accomplished via this study:

- **Specific Aim 1:** To test the feasibility and acceptance of Inner Engineering Online through assessment of participation, compliance, protocol adherence and study satisfaction.
- **Specific Aim 2:** To quantitatively assess the effect of IEO on measures of burnout, stress, and well-being among study participants.
- **Specific Aim 3:** To determine the effect of IEO on measures of well-being among the control-group after they cross-over to the intervention group at the end of first phase.

The study will be conducted in 2 phases. The first phase will accomplish specific aims 1 and 2, while specific aim 3 will be accomplished in the second phase.

References:

1. WHO. Burn-out an “occupational phenomenon”: International Classification of Diseases [Internet]. 2019 May 28. Available from: [https://www.who.int/mental\\_health/evidence/burn-out/en/](https://www.who.int/mental_health/evidence/burn-out/en/)

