### b. *Data Analysis:*

Baseline characteristics of participants will be recorded. Continuous data will be presented as means  $\pm$  standard deviation or median (interquartile range) depending on the distribution of the data and assessed with a parametric or non-parametric t-test, as appropriate. Normality will be assessed with the Shapiro-Wilk test. Categorical data will be presented as frequencies and proportions and assessed with a chi-square or Fisher's exact test. SAS 9.4 (SAS Institute Inc., Cary, NC) will be used for all analyses with two-sided p-values  $< 0.05$  considered statistically significant.

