#### **Analysis of Aim 2:**

Given the continuous nature of the scales used to assess stress, burnout and measures of well-being, differences between groups will be assessed with a parametric or non-parametric t-test. Although we expect that randomization should account for any differences between baseline characteristics, unadjusted and adjusted linear regression may be utilized in order to account for differences that persist. Our primary analyses will be assessed using intention-to-treat principles. In order to assess whether there are differences between baseline and at six weeks, we will employ the use of paired t-tests as appropriate.

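### Aim 2 adds before-after paired t-tests at the 0.05 level without calling them descriptive or making the randomised comparison decisive

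*Combined protocol and SAP*

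**What the plan says.** Specific Aim 2 (section B2) is "To quantitatively assess the effect of IEO on measures of burnout, stress, and well-being among study participants". The Analysis of Aim 2 has four parts:

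- It starts with the randomised comparison: "differences between groups will be assessed with a parametric or non-parametric t-test". It does not say whether end values or changes are compared.
- Regression is optional: "unadjusted and adjusted linear regression may be utilized in order to account for differences that persist".
- On the analysis principle it says: "Our primary analyses will be assessed using intention-to-treat principles". No sentence names which test is primary.
- It ends with a comparison of baseline and six weeks, for which "we will employ the use of paired t-tests as appropriate". It does not say whether this is done within each arm, which is the natural reading, or what the result is for.

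The Data Analysis section states that SAS "will be used for all analyses with two-sided p-values" below 0.05 "considered statistically significant". One threshold therefore covers the between-group and the paired tests alike.

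The Study Procedure section schedules surveys at baseline and 30 days for Group 1, and at baseline, 30 and 60 days for Group 2. The follow-up section adds 60 days for Group 1 and 90 days for Group 2. No survey falls at six weeks.

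**The concern.** The trial randomises a concurrent reading control so that the IEO effect can be separated from whatever else changes over a month. A before-after test discards that control. It responds equally to IEO and to change common to both arms, such as calendar effects, repeat completion of the same self-report scales, or taking part in a study. Two paired tests, one per arm, do not repair this: a significant change in one arm and a non-significant change in the other is not a test of the difference between them.

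Under the plan's single threshold, a paired p-value below 0.05 counts as a significant result under an aim worded as the effect of IEO. The sample size section says the data will be used to power a larger trial. If a before-after improvement that includes shared change were taken as the effect size, that trial would be planned too small.

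**Working it through.** **The plan's own figure.** The only sample size figure is a minimum of 60, justified by feasibility. No effect size, SD, power or dropout is given, so there is no calculation to reproduce.

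**Inputs from the documents.** Minimum enrolment 60; two groups by simple randomisation, ratio not stated; two-sided alpha 0.05 for all analyses.

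**Assumptions.**
- 1:1 allocation, so n = 30 per arm.
- True IEO effect zero.
- The same mean change D, in baseline SD units, in both arms, with D from 0 to 0.5.
- Correlation r between baseline and follow-up of 0.5 to 0.7.

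The documents give no values for D or r, so ranges are shown.

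**Step 1: paired test in the IEO arm.** The SD of change is √(2(1−r)), so the standardised change is dz = D/√(2(1−r)). Power comes from the non-central t with 29 df and non-centrality dz√30. At D = 0.3:
- r = 0.5: dz = 0.3/1.000 = 0.300, non-centrality 1.64, rejection 35.5%.
- r = 0.7: dz = 0.3/0.775 = 0.387, non-centrality 2.12, rejection 53.6%.

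**Step 2: IEO arm significant, control arm not.** With equal rejection probability p in two independent arms, this is p(1−p). At D = 0.3 it is 0.355 × 0.645 = 22.9% for r = 0.5 and 0.536 × 0.464 = 24.9% for r = 0.7. Simulation with 40,000 trials per scenario gave 23.4% and 24.5%.

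**Step 3: between-arm test of change.** In the same simulations it rejected in 4.9 to 5.2% of trials at every D examined.

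| Shared change D (SD) | Paired test, IEO arm | IEO significant, control not | Between-arm test |
|---|---|---|---|
| 0 | 5% | about 5% | about 5% |
| 0.2 | 19–28% | 15–20% | about 5% |
| 0.3 | 36–54% | 23–25% | about 5% |
| 0.5 | 75–93% | 7–19% | about 5% |

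Ranges run over r = 0.5 to 0.7. The third column falls at D = 0.5 because both arms are then usually significant. The paired test passes 50% only when D reaches 0.37 SD (r = 0.5) or 0.29 SD (r = 0.7).

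**Step 4: what baseline adjustment gains.** With 30 per arm, an unadjusted comparison of end values has 80% power for a difference of 0.736 SD (non-central t, 58 df). Adjusting for the baseline score multiplies the residual SD by √(1−r²). At r = 0.6 this is √0.64 = 0.8, and 0.736 × 0.8 = 0.59 SD, ignoring the one degree of freedom spent on the covariate. A comparison of change scores gives 0.736 × √(2 × 0.4) = 0.736 × 0.894 = 0.66 SD.

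**Step 5: the time point.** Six weeks is 42 days and the surveys are at 30, 60 and 90 days. The two-week allowance after day 30 reaches day 44, but it is given for activity diaries and reading logs, not for the surveys.

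**The case against.** The strongest reply is that the test that answers Aim 2 is present and comes first. The paired sentence comes last, and its stated purpose is only to look for differences from baseline. Describing change over time is legitimate, and this is a feasibility study. All of that is correct.

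Three stronger readings are tempting, and the documents do not support them.

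- **That the plan credits IEO with any before-after change.** No sentence says a significant paired test will be read as an IEO effect, or that significance in one arm will be set against non-significance in the other.
- **That a significant paired result is likely even if IEO does nothing.** For a single scale this depends wholly on an assumed shared change: the rate is 5% with none, and exceeds one half only from roughly 0.3 to 0.4 SD. Regression to the mean is a weak argument for such a change, because eligibility sets no minimum stress or burnout score; stressed employees may self-select, but this is not documented.
- **That every trial with exactly one significant arm is misleading.** At 0.3 SD this happens in about 46 to 49% of trials, but in half of them the significant arm is the control.

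The order of sentences does not settle the matter, however. No test is named primary, one threshold covers everything, and the feasibility label does not help when the outcome data are meant to size the next trial.

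**Conclusion.** The point holds as a gap in the plan, not as an error in its main comparison. Aim 2 contains uncontrolled tests under the same significance rule as the randomised comparison, with nothing to rank the two and with baseline adjustment left optional.

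Its size depends on how much both arms change for reasons other than IEO, which the documents do not indicate. With no shared change the paired test has its nominal 5% error. With an assumed 0.2 to 0.3 SD, its rejection rate is between 19 and 54% per scale. These figures rest on 30 completers per arm, zero IEO effect and correlation 0.5 to 0.7. The randomised comparison is protected against shared change throughout. It does not remove an expectation effect confined to participants who know they are receiving IEO, and nothing here claims that it does.

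**What to change.** In the Analysis of Aim 2:

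1. State that the conclusion on the effect of IEO rests only on the between-arm difference at the 30-day survey, estimated by linear regression adjusted for the baseline score of the same scale (ANCOVA). Make this the planned analysis instead of one that may be used.
2. Replace the paired t-tests with mean change from baseline by arm and 95% confidence intervals, labelled descriptive and without p-values.
3. Reconcile the six-week time point with the 30-day survey in the Study Procedure section.

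The Analysis of Aim 3 repeats the paired sentence, and no concurrent comparator is specified there for the crossed-over group. The time point needs the same correction, and the before-after result the same care in labelling.

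The cost is a few sentences and fewer p-values to report. No new data or design change is needed, since the baseline scores are already collected. At an assumed correlation of 0.6, the adjustment lowers the difference detectable with 80% power from about 0.74 to 0.59 SD.

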#### **Analysis of Aim 3:**

To assess the effect of IEO intervention on the control group following its cross-over to the intervention will be assessed using a parametric or non-parametric t-test. Although we expect that randomization should account for any differences between baseline characteristics, unadjusted and adjusted linear regression may be utilized in order to account for differences that persist. Our primary analyses will be assessed using intention-to-treat principles. In order to assess whether there are differences between baseline and at six weeks, we will employ the use of paired t-tests as appropriate.

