### B1. PURPOSE OF PROTOCOL

The purpose of this study is to determine the effects of a web based intervention called “Inner Engineering Online (IEO)” on the burnout states, stress and overall well-being of employees in a company.

The specific aims include:

1. To test feasibility and acceptance of IEO through assessment of participation, compliance, protocol adherence & study satisfaction.
2. To quantitatively assess the effects of IEO on measures of Burnout, Stress & well-being among the participating employees.
3. To determine the effect of IEO on measures of well-being among control employees after they cross over to the intervention group at the end of first phase.

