### B3. DESCRIPTION OF RESEARCH PROTOCOL

#### A. Study Design – Overview, Methods, Procedures

##### Study Overview:

This study involves evaluation of the effects of Inner Engineering Online (IEO) intervention by employing validated questionnaires aiming to measure stress and well-being in the form of a survey to company employees participating in the study.

In order to evaluate this, we randomize the participants into either of the two groups: one who participate in the IEO activities daily for the first 30 days and the other who do not participate in the IEO activities during the first 30 days. We then evaluate stress and burnout along with measures of well-being in these participants using validated electronic instruments at baseline and at the end of the 30 days. This is phase 1 of the study.

For the phase 2, we cross-over the group 2 participants and provide them with the IEO intervention. We follow them through another 30 days and then evaluate measures of stress, burnout and well-being using validated instruments at the end of these 30 days.

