### **Randomization:**

Participants will be randomized into one of the two groups using [Simple Randomization Technique] by REDCap. Participants will be randomized into:

1. Intervention Group: Participants will receive the Inner Engineering Online Intervention for a total of 30 days (4 weeks)
2. Control Group: Participants will read a book/journal of their choice for 25 minutes each day for a total of 30 days (4 weeks)

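### The paired tests for Aims 2 and 3 end at six weeks, when no questionnaire is scheduled; for Aim 3 the only start visit named, baseline, precedes the reading month.

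*Combined protocol and SAP*

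**What the plan says.** The Analysis of Aim 2 and Analysis of Aim 3 sections (B3, Statistical Considerations, Data Analysis) end with the same sentence. To assess "whether there are differences between baseline and at six weeks, we will employ the use of paired t-tests", qualified by a phrase allowing them where suitable.

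The Aim 3 section opens with a different test: the effect of IEO "on the control group following its cross-over to the intervention will be assessed using a parametric or non-parametric t-test". It names no visits and does not say whether the comparison is within Group 2 or between the groups. It then repeats a sentence from Aim 2: "Although we expect that randomization should account for any differences between baseline characteristics", with optional unadjusted and adjusted regression.

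The rest of the protocol sets these times:

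- **Aims.** B1 defines Aim 3 as the effect "among control employees after they cross over to the intervention group at the end of first phase". B2 states: "The first phase will accomplish specific aims 1 and 2, while specific aim 3 will be accomplished in the second phase".
- **Phases.** The Study Overview has phase 1 assessed "using validated electronic instruments at baseline and at the end of the 30 days". For phase 2, after Group 2 crosses over: "We follow them through another 30 days and then evaluate measures of stress, burnout and well-being".
- **Surveys.** Study Procedure schedules Group 1 at baseline and 30 days, and Group 2 at baseline, 30 and 60 days. The 30 day Follow Up section adds the same questionnaires at day 60 for Group 1 and day 90 for Group 2.

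**The concern.** A paired test needs two measurements on the same person. The second one named here, at six weeks, is never collected, so whoever analyses the data must substitute a visit.

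For Aim 2 the substitution is obvious and the consequence small. Phase 1 runs from day 0 to day 30, and the main comparison is between groups.

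For Aim 3 the start visit is open as well. Group 2 begins IEO only after 30 days of reading, so the change that answers the aim starts at day 30. The only start the analysis text gives is baseline, which Study Procedure lists for Group 2 as a visit separate from 30 days. An analyst who keeps baseline and replaces six weeks with the end of phase 2 would test day 0 against day 60. That is one possible reading, not what the plan says. Under it, any change in the reading month that lasts to day 60 would count as an IEO effect. The same data are meant to help power a larger trial (Sample Size Justification).

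**Working it through.** **1. Does six weeks match any questionnaire?**

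Six weeks = 6 × 7 = 42 days.

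| Counted from | Falls on | Group 1 surveys | Group 2 surveys | Nearest survey |
|---|---|---|---|---|
| Baseline | day 42 | 0, 30, 60 | 0, 30, 60, 90 | day 30, 12 days away (day 60 is 18 days away) |
| Crossover (day 30) | day 72 | 0, 30, 60 | 0, 30, 60, 90 | day 60, 12 days away |

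Neither is a survey day.

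**2. Can another provision rescue the label?**

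- *Loose wording for day 30.* No. Under Randomization, "Participants will receive the Inner Engineering Online Intervention for a total of 30 days (4 weeks"), and Study Procedure makes the same equation of 30 days with four weeks.
- *The two-week allowance.* Day 42 lies within 30 + 14 = 44 days, but Study Procedure limits the allowance to activity diaries and reading logs.
- *The Final Survey.* It is sent only after the analysis is finished.
- *Baseline meaning a phase 2 baseline.* The protocol defines none.

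**3. What would a baseline start mix into Aim 3?**

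- Day 0 to day 42: 30 reading days and 12 IEO days, so 12/42 = 29% of the interval is IEO.
- Day 0 to day 60: 30 reading days and 30 IEO days, so 30/60 = 50% is IEO.
- Day 30 to day 60: all IEO.

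**4. How much could it matter? (illustration)**

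From the protocol: two-sided 0.05 (Data Analysis). Assumed, because the protocol gives no figure: n = 30 controls with complete pairs (an equal split of the minimum 60 and no dropout), correlation r between visits, equal variances, no IEO effect, and a shift of δ SD during reading that persists to day 60.

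SD of the paired change = √(2(1 − r)). At r = 0.6 this is √0.8 = 0.894.

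Noncentrality = δ√n / √(2(1 − r)). At δ = 0.2 this is 0.2 × 5.477 / 0.894 = 1.225, with 29 degrees of freedom and critical value 2.045, which gives a rejection probability of 0.220.

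Chance of a significant day 0 to day 60 result:

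| r | δ = 0.1 | δ = 0.2 | δ = 0.3 | δ = 0.4 |
|---|---|---|---|---|
| 0.5 | 0.083 | 0.185 | 0.355 | 0.563 |
| 0.6 | 0.091 | 0.220 | 0.427 | 0.658 |
| 0.7 | 0.105 | 0.277 | 0.536 | 0.780 |

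A simulation at r = 0.6 (200,000 trials per shift, equal correlation between visits) gave 0.091, 0.219, 0.425 and 0.658 for day 0 to day 60, and 0.050 in all four cases for day 30 to day 60.

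**The case against.** The strongest reply is that the intent is plain. The lead Aim 3 sentence ties the test to the period after crossover, B2 places Aim 3 in the second phase, and the Study Overview and Study Procedure bound that phase by the day-30 and day-60 surveys. The six-week sentence comes last, is qualified, and is probably copied from Aim 2. This stands as evidence of intent. It does not put the visits into the analysis text, and the one contrast that does name visits names the wrong ones.

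The error rates belong to a day 0 to day 60 test that the plan does not contain, and every input except the significance level is assumed. The protocol offers no evidence of drift during reading. With 20 complete pairs and r = 0.6 the rates fall to about 8%, 16%, 30% and 48%. All of this is fair: the rates only illustrate the stakes, and the visit mismatch does not depend on them.

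A day 30 to day 60 test remains uncontrolled. If the same shift recurred in month two, it too would reject about 9%, 22%, 43% or 66% of the time. That is correct, and it is why the result should be labelled a within-group change.

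Finally, Group 1 completes the same questionnaires at day 60, so a between-arm reading of the lead Aim 3 test is possible. That also stands. The remark about randomization is therefore out of place only if the test is within Group 2.

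**Conclusion.** The concern holds. The paired contrast in both sections uses a time at which no questionnaire is given, and no other provision supplies one. For Aim 2 this is a visit-label error of small consequence.

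For Aim 3 it should be fixed before analysis. The text leaves the comparator and the visits open, and its only stated start precedes the reading month, contrary to the aim. If day 0 to day 60 were adopted, false-positive rates of roughly 9% to 66% would follow at r = 0.6, against a nominal 5%. Those rates assume 30 complete pairs, no IEO effect and a lasting reading-month shift of 0.1 to 0.4 SD. Confidence in the mismatch is high; the rates are illustrative.

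**What to change.** - **Aim 2.** Replace six weeks with day 30 in the paired test. Leave the between-group analysis as it is.
- **Aim 3.** Replace the contrast with the Group 2 paired change from the day-30 (pre-crossover) survey to the day-60 survey. Report it as an uncontrolled within-group change, and drop the sentence about randomization for this contrast.
- **If a between-arm comparison at day 60 is also intended,** list it separately and note that both groups have had IEO by then.
- **Optional.** Show the Group 2 change from day 0 to day 30 alongside, so that readers can see any movement during reading.

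The cost is wording only, since every survey needed is already scheduled. The Aim 3 effect may look smaller than it would from day 0, and trends that continue past day 30 are not removed.

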### C. Subject Selection

#### Inclusion Criteria:

- Age  $\geq$ 18 years
- Interest in Inner Engineering Online (IEO) Program

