### B2. SIGNIFICANCE AND BACKGROUND FOR THE STUDY

Burnout is described as a syndrome resulting from chronic workplace stress that has not been successfully managed. It is characterized by exhaustion, depersonalization, and reduced professional efficacy. Several studies have evaluated interventions that are aimed at identifying and ameliorating burnout, or components of burnout such as high stress and sleep disturbances. Meditation, specifically, has shown to be an accessible and efficient method for combating stress, burnout, and promoting a sense of well-being.

Inner Engineering Online (IEO) is a web based intervention administered by the Isha Foundation, a not-for-profit, global, volunteer-based organization. IEO is widely practiced around the globe, but lacks a systematic evidence base. The Inner Engineering Online program is a holistic tool for promoting well-being that teaches individuals how to mindfully and effectively respond to daily stressors using yogic sciences. The program offers guided meditation and yoga practices to promote harmonizing mind-body-emotion and energy of the individual while simultaneously promoting mindfulness, joy, and vitality.

Studies reveal that Inner Engineering meditation and yoga practices improve mental clarity, emotional well-being, productivity, and inner peace while reducing perceived stress and compulsive behaviors. These studies suggest that practice of Inner Engineering meditation may be a pragmatic treatment for stress reduction.

S2Tech is a reputed company providing Information Technology (IT) support to businesses in 35 states of United States of America for over 22 years. The company is looking to promote mindfulness and combat burn out and stress in its employees while voluntarily supporting research studies assessing these markers. The Company is offering the standalone Inner Engineering Online (IEO) course from Isha foundation for all its interested employees primarily to combat stress. While the participants are encouraged to participate in this study, research participation is entirely optional for the participants and will not impact their relationship with their employees in any form. The primary purpose is for the company to offer programs to combat stress and research is optional.

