### **Enrollment:**

The recruitment is done by the S2Tech company using flyers for advertisements at the company. The recruitment process also involves awareness campaigns, word of mouth announcements as well as advertising flyers on the social media and official websites of the company.

The research team sends a public survey link, where participants can confirm their interest in the study and get detailed information of the study procedures after the company recruits potential participants during awareness campaigns organized by the company.

If they are interested in participating after receiving the email, they will be directed to REDCap where they will be asked a few screening questions to ensure study eligibility. Participants who are eligible will then be directed to an electronic consent form.

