### **Study Procedure:**

We will be administering a brief survey to willing participants after they provide electronic consent. If a participant decides to participate, they will receive a paper survey to complete, or they can complete the survey online via an anonymous REDCap survey link.

The Isha Foundation (which is responsible for the Inner Engineering Online Course) has agreed to send participants an email which contains detailed instructions on how to perform the IEO intervention after the electronic consent has been signed. The Isha Foundation receives the participating employee emails from the company, as they are the primary instructors for the intervention.

Subjects will be randomized following the consent into two groups.

**Group 1** will be asked to complete the Inner Engineering Online course which includes completing 7 meditation and yoga course modules in a duration of 30 days. They will be given an IEO activity diary and will be asked to keep a track of their progress. The activity diary will be collected from them on a

weekly basis for 30 days.

After 4 weeks (i.e., 30 days) they will be administered the same set of survey questionnaires which was asked before the intervention was administered. All communications will be conducted electronically or via phone.

**Group 2** will be asked to read a book or journal of their choice for 30 minutes at a time for 30 days. They will also be asked to complete a reading log every day to keep a track of their progress every day for 30 days.

Once 30 days is over they will be asked to complete the IEO intervention, which includes practice of meditation and yoga daily for another 30 days while maintaining an IEO activity diary. Group 2 will be asked to complete set of questionnaire at baseline, 30 days and after 60 days.

Surveys will be administered at two time points for group 1 at baseline and at 30 days, whereas three time points for group 2 that is baseline, 30 days and 60 days.

Apart from the surveys, the participants are advised to maintain a reading log or an activity diary for each week. These documents will be collected electronically, either via direct online submission or a scanned copy to be uploaded and sent to a redcap survey link at the end of each week. In order to account for national holidays and personal circumstances, participants may submit their activity diaries and/or reading logs within 2 weeks of the 30 day and 60 day time point.

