## B. Statistical Considerations

### a. *Sample Size Justification:*

In this survey based, randomized cross-over study, we are looking at the feasibility of implementing an Inner Engineering Online Intervention on a group of willing company employees. Since it is a feasibility study, we plan to enroll a minimum of 60 participants. Data from these participants will be used to power a larger trial based on the outcomes such as stress, burnout & overall well-being measured during the course of the study.

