#### Exclusion Criteria:

- Low English proficiency
- Not currently residing in United States

Subjects will be enrolled without regards to race, gender, or vulnerable category status.

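### Eligibility does not exclude current IEO practitioners and prior IEO exposure is not recorded, so the Aim 2 contrast and the Aim 3 change can be diluted by an unknown amount

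*Combined protocol and SAP*

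**What the plan says.** B3.C Subject Selection has two inclusion criteria, age 18 or over and "Interest in Inner Engineering Online (IEO) Program", and two exclusions, "Low English proficiency" and "Not currently residing in United States". Neither list mentions past or current IEO, or any other meditation or yoga practice.

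B2 describes IEO as in wide use worldwide. It says the company offers the standalone course "for all its interested employees primarily to combat stress", with joining the research left optional. An employee can therefore take IEO without entering the trial.

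The Study Overview describes the comparison group as going without IEO for the first 30 days, after which it crosses over. The control procedures consist of daily reading and a reading log. The analysis sections for Aims 2 and 3 specify intention-to-treat, and allow adjusted linear regression for baseline differences that persist.

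**The concern.** Aim 2 asks what IEO does to burnout, stress and well-being, by comparing people given IEO with people not given it. Aim 3 asks what changes when the control group starts IEO. Both need participants who are not already doing IEO at entry.

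For a current practitioner, assignment changes little. In the control arm that person may carry on practising during the control period, and both the baseline and the 30-day score then reflect IEO. In the IEO arm the baseline already contains whatever IEO does, so little change is left to see. Intention-to-treat rightly keeps such people in their assigned arm, so the analysis set does not remove the problem. If prior practice is not recorded, the adjusted regression cannot account for it either.

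Feasibility status does not make this harmless. The Sample Size Justification says the data will be used to power a larger trial, so a diluted estimate would carry forward into that planning.

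**Working it through.** **Does any other section close the gap?**

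- *Enrollment* and *B6 Recruitment*: brief REDCap screening checks eligibility. The questions are not shown, but their stated purpose is the listed criteria, which do not cover IEO practice.
- *Study Overview*: states the intended control condition. It sets no entry check and no washout.
- *Study Procedure* and *Reading Log*: controls log reading. Their IEO diary starts only after cross-over.
- *30 day Follow Up* and *Final Survey*: these ask about IEO practice after the study period, not before it.
- *Data Analysis*: baseline characteristics are to be recorded, but none is named.

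No section excludes, screens for, stratifies by or names prior IEO exposure.

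**Is there a plan figure to reproduce?** No. The minimum of 60 is a feasibility number, given without effect size, SD or power.

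**Size of the dilution (illustration).** Inputs:

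- d, the true effect in people not practising at entry.
- q, the share of each arm currently practising at entry. This is assumed.
- r, the contrast among practitioners as a fraction of d. This is assumed.
- 30 per arm, which is the minimum of 60 split 1:1. The ratio is not stated, so this too is assumed.

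The expected between-arm difference is (1 − q)·d + q·r·d = d·[1 − q(1 − r)]. With r = 0, where practitioners show no contrast, it is (1 − q)·d. The same factor applies to the Aim 3 mean change if practising controls show no change on crossing over.

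The expected number of practitioners is 60q overall and 30q among controls. The chance of at least one among 30 controls is 1 − (1 − q)^30.

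| q (assumed) | Practitioners in 60 | Among 30 controls | Chance of at least one practising control | Effect retained, r = 0 | Effect retained, r = 0.5 |
|---|---|---|---|---|---|
| 5% | 3 | 1.5 | 1 − 0.95^30 = 79% | 0.95 | 0.975 |
| 10% | 6 | 3 | 1 − 0.90^30 = 96% | 0.90 | 0.95 |
| 20% | 12 | 6 | 1 − 0.80^30 = 99.9% | 0.80 | 0.90 |

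Even a small share would probably put at least one practitioner in the control arm. The loss of effect is modest unless q is large.

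**The case against.** The best reply is that the exposure is conjectural. Worldwide use says nothing about the US staff of one IT company. B2 puts the company's offer in the present tense, as the occasion for the study, and does not say that staff had already taken the course. Randomisation spreads practitioners across arms in expectation, so the expected result is dilution and not a spurious effect. All of this stands, and it is why the size is left open. It does not answer the point that the written criteria admit current practitioners while the course is on offer outside the research.

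The Study Overview's description of controls as IEO-free also has some weight, since a practising control might stop. That person's comparison would then be continuing against withdrawing, which is still not the effect of being given IEO.

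A reader might infer several stronger points that the documents do not support:

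- *That requiring interest in IEO selects for existing practitioners.* Someone who has finished the course could be less inclined to enrol. The documents support neither direction.
- *That anyone who ever took IEO can show no effect.* A lapsed user given 30 days of modules and a diary could still respond. The argument holds for current practice, and perhaps for recent completion.
- *That non-employees will be enrolled, because the link is public and there are "advertising flyers on the social media and official websites of the company".* Those are the company's own channels, and the link follows recruitment by the company. The Study Procedure says "The Isha Foundation receives the participating employee emails from the company". B1 states the question as effects "on the burnout states, stress and overall well-being of employees in a company", and the sample size section refers to "a group of willing company employees". The missing employment criterion is a drafting gap.
- *That the trial loses a stated amount of power.* The plan claims none. Dilution by (1 − q) can be turned into a sample-size factor of 1/(1 − q)², but here that factor would rest entirely on an assumed q and on r = 0.

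**Conclusion.** The concern holds for current practitioners. Followed as written, the plan can randomise people already practising IEO and has no named variable by which to identify them afterwards. The expected consequence is dilution of the Aim 2 between-arm contrast and of the Aim 3 change in the control group, plus possible chance imbalance in a sample of about 60.

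The size cannot be stated. Under the zero-contrast assumption the retained effect is (1 − q), and it is larger if practitioners still respond. The documents give no q, and the 1:1 split behind the table is also assumed. This is a specific, inexpensive improvement to the design. It does not show that the results will be materially diluted, and it does not show that the sample will include people from outside the company.

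**What to change.** 1. Add to the Exclusion Criteria in B3.C: *currently practising, or has recently completed, Inner Engineering (IEO)*. The protocol should define *recently*. Add a matching question to the REDCap screener.
2. Record any past IEO and other current or past meditation or yoga practice at baseline, as data and not as grounds for exclusion. Name these in advance as covariates in the adjusted regression for Aims 2 and 3.
3. As an editorial clarification only, list current employment at the company as an inclusion criterion, in line with B1 and the sample size section.

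The cost is a short amendment, one screening question and a few baseline items, with a slightly smaller volunteer pool. If few participants report past exposure, the covariates will be imprecisely estimated but still useful for description.

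The entry exclusion does not stop controls from taking the company-offered course after randomisation. That is a separate problem and needs its own provision.
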